### 2.3.2 Safety Endpoint(s)

The safety endpoints include adverse events (AEs), 12-lead electrocardiogram (ECG), vital signs, laboratory safety data, antibodies to teuglutide, and 48-hour urine output, body weight, body mass index (BMI) and gastrointestinal-specific tests.

### 2.3.3 Pharmacokinetic Endpoint(s)

The following parameters will be derived as described in a separate PK SAP and reported separately:

Area under the plasma concentration–time curve from zero to the last measurable concentration (AUC0–t)

Maximum plasma concentration (Cmax)

Time to Cmax (tmax)

terminal-phase half-life (t1/2)

Apparent clearance (CL/F)

Apparent volume of distribution (V/F)

Document: T:\PROJ\Shire\UYA25606\_Biostatistics\Documentation\SAP\SAP\SHP633-306\_SAP\_Final  
v2.0\_20180415.docx

Author: [REDACTED]

Version Number:  
Version Date:

[figure not shown]
Final V2.0  
15Apr2019

### 3. STUDY DESIGN

#### 3.1 General Description

This is an open-label, multicenter study, consisting of a conditional PN/IV optimization period, a mandatory PN/IV stabilization period, and a 24-week treatment period. A schematic representation of the study design is presented in [Figure 1](#).

**Figure 1: Study Schematic**

##### 3.1.1 Optimization and Stabilization Periods

If at screening, a subject does not have an optimized PN/IV volume, defined as a 48-hour urine output between 2 and 4 L, he/she will enter the optimization period, during which the minimally tolerated stable PN/IV volume will be determined during a period of up to 8 weeks.

All subjects will then enter the stabilization period, during which the target PN/IV volume will be maintained for at least 4 consecutive weeks (8 weeks maximum). Those subjects who fail to stabilize will not proceed further and will not be included in the treatment period.

Schedules of evaluations for the optimization/stabilization period can be found in the protocol.

##### 3.1.2 Treatment Period

Following the stabilization period, subjects will enter a 24-week dosing period, during which all subjects will receive teduglutide 0.05 mg/kg subcutaneously (SC) once daily.

Document: T:\PROJ\Shire\UYA25606\_Biostatistics\Documentation\SAP\SAP\SHP633-306\_SAP\_Final  
v2.0\_20180415.docx

Author: [REDACTED]

Version Number:  
Version Date:

Final V2.0  
15Apr2019

At each site visit during the treatment phase, efficacy (adjustments to PN/IV) and safety will be monitored.

Subjects will have blood samples taken for teduglutide PK analysis at predose and 15, 30 minutes and 1, 2, 3, 4, 6, 8, 10, and 12 hours post dose at the baseline visit (Visit 2).

Subjects will also have blood samples taken for teduglutide PK analysis at predose and 1 and 2 hours post dose at Week 4 (Visit 5) or Week 12 (Visit 7) of the treatment period.

All subjects who complete the study may participate in a long-term extension study in which eligible subjects will continue to receive teduglutide.

Schedules of evaluations for the Treatment Period can be found in the protocol.

### **3.2 Randomization**

Not applicable for this single arm study.

### **3.3 Blinding**

Not applicable for this open-label study.

### **3.4 Sample Size and Power Considerations**

The sample size of the SHP633-306 study is based on patient prevalence and study design elements; no statistical estimation was involved. Possible medical institutes for SBS studies are limited, given the rarity of the disease and the very limited number of patients with SBS (<1000) in Japan. The applicant considers that 5 treated subjects in SHP633-306 should provide sufficient basic information concerning the efficacy, safety and tolerability as well as PK of teduglutide in the Japanese study population.

## **4. STATISTICAL ANALYSIS SETS**

### **4.1 Screened Population**

All subjects who provided a signed Informed Consent Form (ICF) will be included in the Screened Population.

### **4.2 Intent-to-treat (ITT) Population**

The Intent-to-treat Population will include all subjects who are deemed eligible for teduglutide treatment at the baseline visit (Visit 2).

Document: T:\PROJ\Shire\UYA25606\_Biostatistics\Documentation\SAP\SAP\SHP633-306\_SAP\_Final  
v2.0\_20180415.docx

Author: [REDACTED]

Version Number:  
Version Date:

Final V2.0  
15Apr2019

#### 4.3 Per Protocol (PP) Population

The Per Protocol Population will include all subjects in the ITT Population who complete the treatment period without any major protocol violations that could potentially affect the efficacy conclusions of the study. These situations include the following:

- Missing baseline and/or Week 24 for the weekly PN/IV volume efficacy data based on diary data.
- Non-compliance to study drug administration as defined in [Section 5.7](#)

Reasons for exclusion from the PP Population will be presented in the listings for the ITT population.

#### 4.4 Safety Population

The Safety Population will include all subjects in the ITT Population who receive at least 1 dose of study drug.

#### 4.5 Pharmacokinetic (PK) Population

The PK Population will include all subjects who receive at least 1 dose of teduglutide and have at least 1 evaluable post-dose pharmacokinetic concentration value.

### 5. STUDY SUBJECTS

#### 5.1 Disposition of Subjects

The number and percent of subjects in each study analysis population (i.e., Screened, ITT, Safety, PP and PK) will be presented for the Screened Population.

For the ITT and Safety Populations, the number and percentage of subjects who completed or prematurely discontinued the treatment period will be presented. Reasons for premature discontinuation from the treatment period as recorded on the end of treatment page of the electronic case report form (eCRF) will be summarized (number and percentage). The number and percentage of subjects who completed the treatment period and enrolled in the extension study will also be presented. A subject data listing will present subject disposition for the Screened Population.

Inclusion and exclusion criteria violations, if any, will be presented in a listing for the Screened Population.

Document: T:\PROJ\Shire\UYA25606\_Biostatistics\Documentation\SAP\SAP\SHP633-306\_SAP\_Final  
v2.0\_20180415.docx

Author: [REDACTED]

Version Number:

Final V2.0

Version Date:

15Apr2019

## 5.2 Demographic and Other Baseline Characteristics

The baseline and demographic characteristics will be summarized for the ITT, PP, and Safety Populations with descriptive statistics defined in [Section 11.1. Demographic and baseline characteristics to be presented include:](#)

- Age (at informed consent date) in years, both as a continuous parameter and by categories of <45, 45-<65, and  $\geq 65$ .
- Sex
- Race
- Ethnicity
- Height (cm) at the Screening visit
- Weight (kg) at the Baseline visit
- BMI ( $\text{kg}/\text{m}^2$ ) at the Baseline visit

BMI is calculated as weight (kg)/ [height (m)].

The following SBS history information collected at the Screening visit will be summarized with the descriptive statistics defined in [Section 11.1](#) for the ITT, PP and Safety Populations:

- Duration of SBS (years)
- Primary reason for the diagnosis of SBS (Crohn's disease, vascular disease, injury, volvulus, cancer, and other)
- Secondary reason for the diagnosis of SBS (Y/N), secondary reason (Crohn's disease, vascular disease, injury, volvulus, cancer, and other)
- Stoma (Y/N), stoma type (jejunostomy, ileostomy, colostomy, other)

- Remaining colon (Y/N), estimated percent colon remaining, and colon in continuity (Y/N)
- Total estimated remaining small intestinal length (cm) and category (< 25 cm,  $\geq$  25 cm; < 40 cm,  $\geq$  40 cm; < 60 cm,  $\geq$  60 cm)
- Distal/terminal ileum (Y/N) and ileocecal valve (Y/N)
- Method to determine remaining anatomy length (surgery, radiology, and other)

Duration of SBS will be calculated as (Date of ICF Signed – Date of Diagnosis of SBS +1)/365.25.

The following Parenteral Nutrition history information collected at the Screening visit will be summarized with the descriptive statistics defined in [Section 11.1](#) for the ITT, PP and Safety Populations:

- Years since start of PN dependency
- Prescribed weekly PN/IV volume
- Prescribed weekly number of days of PN/IV

Years since start of PN dependency will be calculated as (Date of ICF Signed – Start Date of PN dependency +1)/365.25.

The following Crohn's Disease Evaluation information collected at the Screening visit will be summarized with the descriptive statistics defined in [Section 11.1](#) for the ITT, PP and Safety Populations:

- Medical history of Crohn's disease (Y/N), and current clinical status of Crohn's disease (Active, Inactive)

The following gastrointestinal (GI)-specific testing information collected during the stabilization period will be summarized with the descriptive statistics defined in [Section 11.1](#) for the ITT, PP and Safety Populations:

Document: T:\PROJ\Shire\UYA25606\_Biostatistics\Documentation\SAP\SAP\SHP633-306\_SAP\_Final v2.0\_20180415.docx

Author: [REDACTED]

Version Number:  
Version Date:

Final V2.0  
15Apr2019

- For subjects with Crohn's disease, upper GI contrast series with small bowel follow-through: normal, abnormal not clinically significant, abnormal clinically significant
- abdominal ultrasound: normal, abnormal not clinically significant, abnormal clinically significant
- colonoscopy: normal, abnormal not clinically significant, abnormal clinically significant
- sigmoidoscopy: normal, abnormal not clinically significant, abnormal clinically significant
- Esophagogastroduodenoscopy (EGD): normal, abnormal not clinically significant, abnormal clinically significant

Colonoscopy, sigmoidoscopy and EGD will also be presented at Dosing Week 24/early termination (ET).

Partial dates for the start date of PN dependency and date of diagnosis of SBS will use the first day of the month if only the day is missing. If both the day and month are missing, the first of January will be used.

### 5.3 Medical History

Medical and surgical history will be coded using the Medical Dictionary for Regulatory Activities (MedDRA). Investigator verbatim as well as preferred terms (PT) and system organ class (SOC) will be included in the listings. The medical history will be summarized by SOC and PT within SOC for the Safety Population, with SOC sorted alphabetically and PT within SOC by descending incidence.

### 5.4 Prior Treatment and Medication

Prior medications will be coded using the World Health Organization Drug Dictionary.

Prior medications are defined as medications taken prior to the first dose of study medication. Partial date imputation for medications is described in [Section 11.5.2](#).

Document: T:\PROJ\Shire\UYA25606\_Biostatistics\Documentation\SAP\SAP\SHP633-306\_SAP\_Final  
v2.0\_20180415.docx

Author: [REDACTED]

Version Number:

Final V2.0

Version Date:

15Apr2019

Prior medication use will be summarized by preferred name using the number and percentage of subjects for the Safety Population. Medications will be sorted by descending incidence by preferred name. Subjects with multiple occurrences of a medication in preferred name will only be counted once within each preferred name. A listing of all medications, both prior and concomitant, will be presented. The listing will be sorted by subject identifier and will include preferred name, reported name, dose, route of administration, dosing frequency, start date, end date, indication, and type of medication (prior only, concomitant only, prior and concomitant).

## 5.5 Concomitant Treatment and Medication

Concomitant medications will also be coded using the World Health Organization Drug Dictionary.

Concomitant medications are defined as medications with onset dates on or after the first dose of study medication, medications with onset dates prior to first dose of study medication without a stop date, or medications with a stop date after first dose of study medication. Partial date imputation for medications is described in [Section 11.5.2](#).

Concomitant medications will be summarized in the same way as prior medications (refer to [Section 5.4](#)).

Diagnostic, surgical, or therapeutic procedures during the study will be listed.

## 5.6 Exposure to Investigational Product

The extent of exposure is defined as the number of days on treatment, including any periods of temporary dose interruption, calculated as:

(date of last dose - date of first dose) + 1.

The first dose date and last dose date will be based on the eCRF. The extent of exposure, the number of days that the dose was administered, will be summarized with the descriptive statistics defined in [Section 11.1](#). The number and percentages of subject will be tabulated for extent of exposure categorized into weeks (<4, 4-<12, 12-<24,  $\geq$ 24). Exposure summaries will be presented for the ITT, PP and Safety Populations.

## 5.7 Measurements of Treatment Compliance

Percent compliance will be calculated as 100 times the number of doses administered (either by the investigator or by the subject per instructions) divided by the number of days on treatment, excluding any periods of temporary dose interruptions due to adverse event that were deemed necessary by the investigator. Number of days on treatment is then calculated as (last dose date – first dose date +1) and the number of days of dose interruption due to adverse event will be excluded, i.e., the sum of (Date of study drug resumed – start date of interruption due to adverse event +1) as recorded on the Study Drug Interruption eCRF form. The information whether the study treatment was administered per instructions is captured on the study drug administration daily diary.

Drug accountability information, first dose date, last dose date, and study medication interruptions (start date of interruption, date study medication resumed, and reason for interruption) will be included in the listings.

Subjects will be considered compliant overall for study medication if the calculated compliance is  $\geq 80\%$ . Overall treatment compliance will be presented for both percent compliance calculations using the descriptive statistics defined in [Section 11.1](#) and the number and percentage of subjects who are  $\geq 80\%$  compliant for both the ITT, PP and Safety Populations. Treatment compliance by visit will not be calculated.

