# 6. EFFICACY ANALYSES

All efficacy analyses will be based on the ITT Population and PP Population and be displayed in tables side by side for these two populations. The PP Population will be used for sensitivity analysis purpose. Unless stated otherwise, the baseline for all efficacy analyses will be as defined in [Section 11.2](#).

All efficacy analyses will be descriptive only and there will be no statistical testing.

Document: T:\PROJ\Shire\UYA25606\_Biostatistics\Documentation\SAP\SAP\SHP633-306\_SAP\_Final  
v2.0\_20180415.docx

Author: 

Version Number:  
Version Date:

Final V2.0  
15Apr2019

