Version Date:

Final V2.0  
15Apr2019

Individual data listings will be sorted and presented by subject number and visit/event date.

Dates will be presented in a DDMONYY format. Dates with partial missing data will be presented with a dash (i.e., '-') for the missing data (e.g., --JAN2019).

In general, analyses on PP population will be conducted if PP population is different from ITT population.

For the following analyses, data for ITT, PP and Safety will be presented side by side in tables:

- Demographic and other baseline characteristics
- Short bowel syndrome history
- Parenteral nutrition history
- Crohn's disease evaluation
- Gastrointestinal specific testing
- Exposure of investigational product
- Treatment compliance

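### SAP 5.7 subtracts one dosing day too many for each adverse-event interruption after which dosing resumed, so percent compliance is slightly overstated and can exceed 100%

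*SAP*

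**What the plan says.** SAP v2.0 Section 5.7 sets the numerator as follows: "Percent compliance will be calculated as 100 times the number of doses administered". For the denominator, "Number of days on treatment is then calculated as (last dose date – first dose date +1"), and from this "the number of days of dose interruption due to adverse event will be excluded". The excluded days are "the sum of (Date of study drug resumed – start date of interruption due to adverse event +1"), with both dates taken from the interruption form of the eCRF. The same section names the two dates again among the items to be listed: "start date of interruption, date study medication resumed, and reason for interruption". A subject with calculated compliance of at least 80% counts as compliant. No cap at 100% is given.

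SAP Section 4.3 uses the result. One ground for exclusion from the PP Population is "Non-compliance to study drug administration as defined in" Section 5.7.

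The formula is the same in SAP v1.0, and the revision history lists no change to Section 5.7.

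**The concern.** Adding 1 to a difference of dates is right when both end dates belong to the interval being counted. That holds for first and last dose, since both are dosing days. It does not hold for an interruption whose end is recorded as the day dosing resumed, because that day is not part of the gap. The formula then takes a day out of the denominator while its dose stays in the numerator.

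Three things follow:

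- The printed percentage is too high for each subject with a resumed adverse-event interruption.
- A subject who took every dose outside the interruption is shown above 100%.
- A subject just under 80% can be scored as compliant and, on this ground, be kept in the PP Population. With 5 treated subjects, one changed status is 1/5 = 20% of the sample.

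**Working it through.** The plan states no compliance figure, so there is none to reproduce. The check applies the formula to constructed cases.

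**Inputs**

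- S, days from first to last dose inclusive: 24 weeks × 7 = 168, once-daily dosing (SAP 3.1.2). Values of 84 and 28 are also used, as assumed early stops.
- L, days actually missed in one resumed adverse-event interruption.
- d, doses taken.
- Assumption: the start date is the first day without drug and the resumption date is the first day back on drug. Resumption minus start then equals L, and the SAP expression equals L + 1.

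**Formulas**

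- As written: 100 × d / (S − L − 1)
- Without the +1: 100 × d / (S − L)
- Difference: 100 × d / [(S − L)(S − L − 1)]

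**Every dose outside the interruption taken, so d = S − L**

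| Case | As written | Without the +1 |
|---|---|---|
| S = 168, one 1-day interruption | 167/166 = 100.6% | 167/167 = 100.0% |
| S = 168, one 5-day interruption | 163/162 = 100.6% | 163/163 = 100.0% |
| S = 168, one 14-day interruption | 154/153 = 100.7% | 154/154 = 100.0% |
| S = 168, two 7-day interruptions | 154/152 = 101.3% | 154/154 = 100.0% |
| S = 84, one 5-day interruption | 79/78 = 101.3% | 79/79 = 100.0% |
| S = 28, one 5-day interruption | 23/22 = 104.5% | 23/23 = 100.0% |

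The excess is one day per interruption. The value passes 100% only when other missed doses are fewer than the resumed interruptions. With one 7-day interruption over 168 days, one other missed dose gives 160/160 = 100.0% and two give 159/160 = 99.4%.

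**Size of the shift.** For S = 168, L from 1 to 14 and corrected compliance from 79.5% to 100%:

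- The smallest shift is at L = 1, d = 133: 100 × 133/(167 × 166) = 0.480 points.
- The largest is at L = 14, d = 154: 100 × 154/(154 × 153) = 0.654 points.

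**The 80% cut-off.** A status changes when d < 0.8 × (168 − L) and d ≥ 0.8 × (167 − L). This range is 0.8 wide, so it holds at most one whole number, and none when 168 − L is a multiple of 5.

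| L | d that changes status | Other missed doses | Without the +1 | As written |
|---|---|---|---|---|
| 1 | 133 | 167 − 133 = 34 | 133/167 = 79.6% | 133/166 = 80.1% |
| 7 | 128 | 161 − 128 = 33 | 128/161 = 79.5% | 128/160 = 80.0% |
| 14 | 123 | 154 − 123 = 31 | 123/154 = 79.9% | 123/153 = 80.4% |

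Of the 14 lengths from 1 to 14 days, 11 have exactly one such dose count and 3 (L = 3, 8, 13) have none. Each change needs 31 to 34 missed doses outside the interruption.

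**Other meanings of the dates** (S = 168, one 7-day gap, 161 doses; correct value 161/161 = 100.0%)

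| Start date holds | Resumption date holds | As written |
|---|---|---|
| first day off drug | first day back | 161/160 = 100.6% |
| first day off drug | last day off drug | 161/161 = 100.0% |
| last dosing day | first day back | 161/159 = 101.3% |
| last dosing day | last day off drug | 161/160 = 100.6% |

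Only the second row gives the right answer, and there the field name would not fit its content.

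**Interruptions never resumed** are outside the point. They have no resumption date and lie after the last dose date, so the denominator already leaves them out.

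**The case against.** The strongest objection is that the dates come from a form that is not in the documents. The error is 0, 1 or 2 days per interruption depending on how sites were told to fill it in, and the SAP cannot alter what was entered. If the resumption field held the last day off drug, dropping the +1 would subtract a day too few. This stands as a condition. It does not restore the formula, because the zero-error case contradicts the field's name, which Section 5.7 uses twice without defining it.

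A value above 100% is also not strictly impossible. Protocol 6.2.2 asks only that doses be at least 12 hours apart, so two doses could fall on one calendar day. That is true, but it departs from once-daily dosing, and the formula exceeds 100% without it.

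The practical effect is small, and this stands in full:

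- PP requires completion of the treatment period, so the 28-day and 84-day cases, read as early stops, could not affect PP. They touch only the ITT and Safety compliance columns.
- A status change needs one exact dose count, and a subject missing over 30 doses might be excluded from PP on other grounds.
- SAP Section 6 limits the role of PP: "The PP Population will be used for sensitivity analysis purpose". Section 11.1 adds: "In general, analyses on PP population will be conducted if PP population is different from ITT population".
- All efficacy analysis is descriptive, and the interruption dates are listed, so a reader could recalculate.

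Finally, Protocol 6.5 defines compliance by planned doses. If 168 were planned, the 14-day case is 123/168 = 73.2%, non-compliant with or without the +1. That is a different denominator and does not make the one in Section 5.7 correct.

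**Conclusion.** The point holds, as a minor error. Section 5.7 sets out to exclude the days of interruption and, on the plain meaning of its two dates, excludes one dosing day more for each resumed adverse-event interruption. The bias is always upward. It is about half a percentage point per interruption of 1 to 14 days over a full course, and larger with shorter exposure or several interruptions. It can print values above 100% in the compliance tables. An unwarranted pass at 80% is possible but rare. ITT efficacy results do not depend on it.

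The conclusion assumes that the start date is the first day without drug and the resumption date the first day back on it. The arithmetic is certain; the field meanings are inferred from their names.

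**What to change.** In SAP Section 5.7, count adverse-event interruption days as date study drug resumed minus start date of interruption, without the +1. State there that the start date is the first day without drug and the resumption date the first day back on drug. Before finalising, check both definitions against the eCRF completion instructions. If the form uses another convention, fit the formula to it so that only days without drug are removed. Keep the +1 in last dose date minus first dose date, where it is correct.

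The cost is a few words in the SAP and one line of code. No new data are needed and ITT results do not change.
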